5.7.1 Index Procedure Details

Refer to the Instructions for Use for a description of the procedure. The following data will be collected on all subjects during the index procedure and prior to discharge on the Index Procedure case report form:

- Summary of symptoms from physical examination
- Endoscopic imaging study
- The EndoRotor® achieved the attempted resection of the targeted lesion(s).
- The EndoRotor® pathological specimens were able to be interpreted by GI pathologists and enabled the rendering of clinical diagnoses.
- The total number of recurrent lesions treated with the EndoRotor.
- Time from scope insertion to scope removal.
- EndoRotor time from resection start to resection end.
- Adverse event assessment and treatment (i.e. delayed bleeding, presence of perforations). Note: Typical and routine steps (endoscopic clipping/mucosal apposition) will be taken to close perforations if they are discovered.
- Ease of use and overall satisfaction with the EndoRotor® System.
- Identification of technical difficulties and device malfunction, if any.
- Photographs post-EndoRotor treatment.

Current standard of care does not guarantee pathology in recurrent lesion procedures due to the difficulty to remove they often are treated with avulsion or Argon Plasma Coagulation. Since the EndoRotor retrieves specimen it can be sent for histopathological review. Although the EndoRotor is not intended for biopsy in this study pathologist will also be able to evaluate specimen that would normally be ablated. Resected tissue collected in the Specimen Trap will be placed in 10% Formalin and sent to the resident pathologist for histological evaluation. The

following steps will be taken for the review and interpretation of the specimens from the Specimen Trap following the procedure:

- 1. The resident pathologist shall be responsible for the preparation of the histology slides and the review and interpretation of the slides per hospital standard operating procedures.
- 2. The prepared specimen will be de-identified per hospital procedure and shipped by courier to an independent pathologist.
- 3. An independent pathologist selected by the Sponsor will prepare histology slides to assess the quality of the specimens.
- 4. The independent pathologist will document his/her assessment of the quality of the specimens.
- 5. Results of the independent pathologist's assessment will be documented on the Histopathology Log within **30 days** of receiving the specimens and uploaded to the Sponsor's secure web server. The table will include site number, patient number, date of receipt, date of analysis, the analysis result, and the date the specimen was returned to the research center.
- 6. The slides will be shipped back to the hospital pathologist by courier for retention per hospital procedures.

5.8 90-Day Follow-Up (+/- 14 days)

- Assessment of symptoms and adverse events
- Using standard of care endoscopy, record the presence of persistent lesions. Determine % of tissue persistence of EndoRotor cases.
- Using standard of care endoscopy, record resection-associated stenosis.
- Assessment of the presence of post polypectomy syndrome.
- Independent quality assessment of pathology specimens by independent pathologist.

6.0 ADVERSE EVENTS

Adverse events will be recorded and documented throughout the duration of the study. In this study, adverse events related to the device or procedure, serious adverse events and Unanticipated Adverse Device Effects will be recorded. Adverse events (AE) unrelated to the device will not be documented on the CRF.

The Investigator at each participating center is ultimately responsible for reporting applicable adverse events to the Sponsor. The adverse event case report form (CRF) will be used to record

adverse event data. The adverse event CRF for a given visit must report all device-related and procedure-related adverse events that have occurred since the last documented visit.

The Sponsor shall review all adverse events for their severity, relationship to the study device(s) and comparative anticipated safety event rates. The Sponsor will conduct evaluations of any unanticipated device-related event per standard operating procedures.

6.1 Adverse Event (AE)

Adverse Events (AEs) are clinical findings that result in an untoward medical event, unintended disease or injury, or any untoward clinical signs (including an abnormal laboratory finding) in subjects, users, or other persons, regardless of whether or not it is related to the investigational medical device. Adverse events will be classified as to severity (mild, moderate, severe), Anticipated (anticipated, not anticipated) and device and procedure relationships. Adverse events will further be categorized as either serious or non-serious.

The following definitions for rating severity of adverse events will be used:

Mild: Awareness of signs or symptoms, but easily tolerated; are of minor

irritant type; causing no loss of time from normal activities; symptoms would not require medication or a medical evaluation; signs or

symptoms are transient.

Moderate: Interferes with the subject's usual activity and/or requires symptomatic

treatment.

Severe: Symptom(s) causing severe discomfort and significant impact of the

subject's usual activity and requires treatment.

AEs or SAEs will also be classified as to their relationship to the device and procedure as follows:

Not Related: The event is due to an underlying or concurrent illness or effect of another

device, drug or intervention and is not related to the investigational

device, procedure or general surgery.

Possible: The event has a strong temporal relationship to the use of the

investigational device, procedure or general surgery, and an alternative

etiology is equally or less likely.

Probable: The event has a strong temporal relationship to the use of the

investigational device, procedure or general surgery and another etiology

is unlikely or significantly less likely.

Definite: An event that can only be attributed to the use of the

investigational device, procedure or general surgery.

Not Assessable: The event's relationship to the use of the investigational device, procedure or general surgery cannot be assessed.

For purposes of this study, the following events are not considered adverse events because they are normally expected to occur in conjunction with endoscopic procedures / post-procedure, or are associated with customary, standard care of subjects undergoing these procedures:

- Early post-procedural pain (within 24 hours post-study procedure) related to the procedure or position on procedure table
- Post-anesthesia/conscious sedation emesis, nausea, or headache (within 24 hours post-study procedure)
- Low grade temperature increase (≤38°C/≤101.4°F)
- Systolic or diastolic blood pressure changes that do not require treatment or intervention
- Any pre-planned surgical procedures

This listing of events is intended to provide guidance to the study sites for purposes of adverse event reporting. The Investigator at the study site should utilize his/her own clinical judgment in evaluating adverse experiences and may decide that the above events should be reported as adverse events.

6.1.1 Serious Adverse Event (SAE)

A serious adverse event (SAE) is defined as an adverse event that:

- Is life threatening or fatal;
- Results in permanent impairment of a body structure or function;
- Results in congenital anomalies/birth defects
- Requires or prolongs hospitalization; or
- Requires medical or surgical intervention to preclude permanent impairment of a body function or permanent damage to a body structure.

Any other important medical event that may not result in death, be life threatening, or require hospitalization, may be considered a serious adverse experience when, based upon appropriate medical judgement, the event may jeopardize the subject or may require an intervention to prevent one of the outcomes listed above.

Delayed bleeding and perforations are the most serious adverse events associated with the resection of mucosal lesions, regardless of technique employed. Each requires the physician to identify it (the source of bleeding or the perforation) and swiftly act in a clinically appropriate manner to rectify the situation. Severe bleeding requires finding the source of bleeding and either using hemoclips or electrocautery to stop the flow of blood. Perforations, once identified

as such, can be treated using specialized endoscopic clips to approximate the edges and eliminate the perforation. Unidentified severe bleeding can result in anemia (decrease in the Hemoglobin and Hematocrit blood counts) with confusion, lethargy, and irritability, as well as hematemesis and hematochezia (bloody stools). Unidentified colon perforations can result in free air within the peritoneum causing compression of vascular structures (vena cava), abdominal distention, discomfort and pain, as well as sepsis and decreased cardiac output and death. Patients need to be made aware of the seriousness of not feeling well after resection of tissue and encouraged to immediately return to the hospital for evaluation.

NOTE: Planned hospitalization for a pre-existing condition or a procedure required by the study plan, without serious deterioration in health, is not considered a serious adverse event.

NOTE: Hospitalization is defined as any initial admission (even if less than 24 hours) to a healthcare facility as a result of a precipitating clinical adverse effect; to include transfer within the hospital to an intensive care unit. Hospitalization or prolongation of hospitalization in the absence of a precipitating, clinical adverse effect (e.g., for a preexisting condition not associated with a new adverse effect or with a worsening of the preexisting condition; admission for a protocol-specified procedure) is not, in itself, a serious adverse effect.

6.1.2 Unanticipated Adverse Device Effects (UADE)

If an SAE is determined to be probably or definitely related to the investigational device and has not been previously anticipated, the clinical finding would further be classified as an unanticipated adverse device effect (UADE). A UADE is defined as "any serious adverse effect on health or safety or any life-threatening problem or death caused by, or associated with, a device, if that effect, problem, or death was not previously identified in nature, severity, or degree of incidence in the investigational plan or application (including a supplementary plan or application), or any other unanticipated serious problem associated with a device that relates to the rights, safety, or welfare of subjects."

All SAE/UADEs must be reported to the IRB in accordance with institutional policies. The Investigator will note whether the adverse event was device-related or procedure-related and the severity of the event. All SAE/UADEs must be reported to Interscope within 24 hours of knowledge of the event.

Any Device Malfunction and/or Failure shall be documented in the CRFs.

6.2 Adverse Event Reporting Requirements

6.2.1 General Reporting Requirements

For the purposes of this study, only device-related and procedure-related serious adverse events, including unanticipated, will be recorded and documented on the Adverse Event CRF throughout the duration of the study. The report should include, but not limited to: severity, duration, action

taken, treatment outcome, seriousness, concomitant medications, pre-existing conditions and relationship of the adverse experience to the study device and procedure.

All AE's should be followed until the event is resolved or judged to be clinically stable. The clinical site should plan to provide additional, relevant AE follow-up information to the Sponsor upon request.

6.2.2 Reporting Requirements for Serious Adverse Events

All serious adverse events must be reported by the Investigator (or designee) to the Sponsor, within **24 hours** of becoming aware of the event.

The Investigator (or designee) must complete the Serious Adverse Event CRF within seven (7) working days of the initial report. The minimum required data to be recorded for an SAE includes: date of event, type of event, duration of event, severity, seriousness, action taken, outcome and, if appropriate, causality and possible relationship to the Interscope EndoRotor® System. In the case of a USADE, when possible, the device involved in the failure or malfunction is to be returned to the Sponsor for analysis.

All SAE's should be followed until the event is resolved or judged to be chronically stable. The clinical site should plan to provide relevant AE follow-up information to the Sponsor upon request.

In the case of serious adverse events, procedure and / or device observations, malfunctions or failures medical record documentation (e.g., procedure notes, operative notes, discharge summary, relevant progress notes, imaging, or lab studies) must be provided to Interscope or its designee.

It is the responsibility of the Investigator to inform the IRB of serious adverse events as required by the IRB policies and in conformance with local regulatory requirements. Any serious adverse device effects and all deaths regardless of cause must also be reported to the IRB per local IRB requirements, and documentation of the report sent to Interscope or its designee.

The Sponsor or its designee will report all applicable serious adverse events and device incidents as post-market vigilance reports per FDA Regulations. The Sponsor will decide whether all of the local Investigators need to be informed immediately of an SAE or SADE, or whether this can be postponed until the next regularly scheduled study update.

6.2.3 Treatment Failure & Device Malfunction Reporting

All reported device observations, malfunctions or failures of the Interscope EndoRotor® System are required to be documented in the Case Report Form. In the event of a suspected observation or device problem, the study device shall be returned to the Sponsor for analysis via Interscope's

Complaint System. Instructions for returning the study device shall be provided to the Investigator.

7.0 RISK/BENEFIT ASSESSMENT

The Interscope EndoRotor® System has been cleared under the Pre-Market program as a 510(K) and certified with the CE Mark and is approved for commercial use wherever the CE Mark is recognized. The device's safety and performance have been established through extensive design verification and validation testing, including prior human use, and through a detailed risk analysis process per 21 CFR Part 803. Interscope does not anticipate new risks to be identified through this clinical study. A summary of the benefits and risks identified are provided below.

The main complications found to be associated with polypectomy appear to be bleeding/hemorrhage, perforation, and post-polypectomy syndrome, which are reported to occur in 0-10.8%, 0-2.3%, and 0.14-3.7% of patients, respectively. Deaths have been reported in only 2 studies, at a rate of 0.01% and 0.1%. The greatest risk factor for an adverse event is associated with increasing polyp size.

The EndoRotor® holds the promise to improve the resection of mucosal-based lesions in the GI tract (stomach, small and large intestines) by making the resections more precise, quicker and more comprehensive. Because of its design, the EndoRotor® suctions in mucosa and then cuts it (about 1750 times a minute) to quickly remove mucosal disease. This quick cutting action allows the user to precisely define the resection margins, allowing all gross visible disease to be removed. User errors tend to increase when fatigue increases. Reducing the procedure time from an hour to several minutes can help to reduce the fatigue associated with mucosal resections. There is the potential that we could see a reduction in persistent lesions (meaning better initial comprehensive removal of disease) when the EndoRotor® is used as the resection tool, meaning that in the future the necessity for second-look procedures could be reduced or eliminated, further decreasing patient morbidity. Because the EndoRotor® was engineered to be a simple device (it only resects mucosa), most users feel comfortable after a few attempts, narrowing the performance gap between an expert endoscopic proceduralist and one who is still in training. The ease with which physicians learn to use the EndoRotor® could also result in less patient morbidity.

7.1.1 Risk Minimization

As with any endoscopic procedure, appropriate safety precautions will be followed. In addition, this protocol provides additional steps to minimize risk to study subjects. These include the following:

- Investigator Selection: The Investigators in this study are selected based on their experience in performing endoscopic treatment procedures, including resection of mucosal tissue.
- Investigator Training: All investigators shall be trained on the use of the EndoRotor[®] to develop a base level of proficiency prior to the execution of the protocol.

- Subject Screening: Careful subject selection as per device Instructions for Use and per study selection criteria.
- Objection by minors or incapacitated subjects: Minors or those patients who are incapacitated and cannot consent for themselves are not included in this study.

7.2 Justification for the Study

This study is justified because additional safety and performance data on the Interscope device is desirable on a larger number of subjects for comparison to other commercially available devices. Risks have been minimized through previous clinical experience in humans on a post-market basis, through device safety and performance testing, Investigator training, and through closely controlled conditions under this study.

7.4 Incentives (if applicable)

Subjects will not be offered any incentives to participate in this study.

8.0 STATISTICAL ANALYSIS PLAN

The analysis of the data from this study will be primarily descriptive. Continuous endpoints will be summarized by N, mean, standard deviation, median, minimum, and maximum. Categorical or binary endpoints will be summarized by N and percentage with confidence intervals as appropriate.

8.1 Population Demographics

The demographics and medical history will be presented in tabular form for all subjects enrolled in this study. Means, standard deviations, and Ns will be used to summarize continuous characteristics such as age. Percentages and counts of subjects exhibiting a characteristic will be used to summarize categorical characteristics such as gender.

8.2 Analysis Populations

Two analysis populations are defined for this protocol, Intent to Treat and Per Protocol.

Intent to Treat Population: All subjects in whom the EndoRotor was used for any resection of a lesion. This includes those subjects that were either treated with the EndoRotor alone or with another adjunctive modality.

Per Protocol (PP): Subset of the Intent to Treat population including those subjects who had complete lesion resection with the EndoRotor alone without any adjunctive modality resection, did not have inclusion/exclusion protocol deviations and completed the 90 day follow up visit. The effectiveness analyses will be conducted on the per protocol population.

Safety Population: Defined as all subjects who were treated with the device.

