	the Interscope, Inc. Quality Management System. Interscope, Inc. is ISO 13485 certified (FM 61310).		
Study Design:	Post-market, prospective, non-randomized, multi-center study for the treatment of subjects with the need for resection of recurrent flat or sessile colorectal lesions where EndoRotor is the primary resection modality of persistent adenoma with a scarred base.		
Enrollment:	Total enrollment is at least 60 evaluable subjects at up to 15 clinical sites		
	I .		

	in the United States and Europe.				
Subject Population:	Adult subjects aged ≥18 to ≤85 years who have one or more recurrent				
	flat or sessile rectal/colon mucosal polyps measuring up to 6 cm in				
	diameter and/or length.				
Estimated Study	First subject enrolled: June 2019				
Duration:	Last subject enrolled: December 2019				
	Study completion (final 90-day visit, closeout visit): June 2020				
Primary Endpoints:	Primary Effectiveness Endpoint (Performance):				
	Technical Success, defined as the ability of the EndoRotor device to				
	resect recurrent flat or sessile colorectal lesions without concomitant use				
	of other resection modalities for mucosectomy and no definitely or				
	probably device-related serious adverse events (SAEs) throughout the				
	90-day follow-up period.				
	Primary Safety Endpoint:				
	Assessment of Serious Adverse Events (incidence, relationship to device				
	and severity) at index procedure and at 90 days, post-procedure.				
Secondary Endpoints:	2 2 2				
v I	and/or photographs and in addition to diagnostic assessment of				
	specimen graded by the independent pathologist.				
	2. Presence of colon stenosis based on endoscopy film and/or				
	photographs.				
	3. Rate of persistence of disease at the location of resection at 90 days.				
	4. Histologic assessment of the diagnostic value of the collected				
	specimens.				
Primary Analysis:	The Per Protocol (PP) analysis population will be the primary				
	effectiveness analysis population.				
Inclusion Criteria:	1. Subjects aged ≥18 to ≤85 years.				
	2. At least one recurrent flat or sessile colorectal lesion measuring up to				
	6 cm in diameter and/or length. 3. Presence of recurrent flat or sessile lesion where the EndoRotor®				
	may be used to resect recurrent neoplasia.				
	4. Favorable anatomy that allows the investigator to access the lesion.				
	5. Subject is able and willing to comply with site standard medical				
	follow-up, including the 90-day follow-up visit.				

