4.0 STUDY ENDPOINTS AND SUBJECT POPULATION

4.1 Primary Endpoints

Primary Effectiveness Endpoint (Performance):

Technical Success, defined as the ability of the EndoRotor device to resect recurrent flat or sessile colorectal lesions without concomitant use of other resection modalities for mucosectomy and no definitely or probably device-related serious adverse events (SAEs) throughout the 90-day follow-up period.

Primary Safety Endpoint:

Assessment of Serious Adverse Events (incidence, relationship to device and severity) at index procedure and at 90 days, post-procedure.

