5.7 Index Procedure

All patients will receive the EndoRotor® treatment following the technique described by Interscope's Instructions for Use.

The mucosal resections are performed during standard flexible colonoscopy procedures. All medications given, pre- and post-procedure precautions and follow-up assessments are part of routine standard of care. This protocol concerns itself with the actual removal of the mucosal lesion once the abnormal area is identified using the colonoscope.

- Patients will be prepped in the usual manner for lower GI endoscopy prior to their interventional visit.
- The procedures will be performed with either Propofol sedation or under general anesthesia.
- When a mucosal lesion is found, the EndoRotor® system will be prepared by attaching the EndoRotor® catheter, foot pedal and the calibrated suction to the Control Unit, ensuring there is a filter in the collection unit (specimen trap), and then priming the catheter with 0.9% normal saline.
- Lesions will be injected using saline solution with dye such as Indigo carmine or Methylene Blue. Indelible ink (such as SPOT) will be injected into the region of the resection to identify the site after resection.
- The EndoRotor® catheter will be inserted through the working channel of the endoscope until it is in proper cutting position with the cutting surface oriented towards the mucosal lesion and the catheter no more than 3cm out of the scope. The physician will turn the motor on by depressing the blue pedal and engage cutting by holding the orange pedal for as long as he/she wishes to cut tissue.
- Cutting should be performed while moving the EndoRotor® catheter. The endoscopist will take care to not keep the suction activated when he/she is not intending to cut mucosa and when stopped for more than 1 second while apposed to tissue to not risk creating a perforation.
- Various techniques can be used to remove the lesion. Recurrent, flat or sessile lesions will be attempted to be removed entirely with the EndoRotor® with no other treatment modalities. The physician will utilize the recommended technique appropriate to the lesion until there is no longer visible evidence of mucosal lesion. The intent of the protocol is to complete lesion resection using the EndoRotor as the only treatment modality. However, should it prove not feasible to complete the resection with the EndoRotor, the investigator may convert to the use of an alternative resection modality.

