8.4 Primary Endpoint Analysis

The primary analysis will be completed on the Per Protocol population and will consist of all evaluable subjects enrolled in the study who have documented recurrent flat or sessile colorectal lesions up to 6 cm in diameter and/or length and are treated with the Interscope device without adjunctive modality. The analysis will be conducted on the percent of lesions with persistent disease. The primary endpoint is:

Technical Success, defined as the ability of the EndoRotor device to resect recurrent flat or sessile colorectal lesions without concomitant use of other resection modalities for mucosectomy and no definitely and probably device-related serious adverse events (SAEs) throughout the 90-day follow-up period.

This analysis population will be used to describe the primary effectiveness and the secondary endpoints. A confidence interval for the successful removal of all lesions will be calculated by Clopper-Pearson exact methods⁶ if all subjects are treated for one lesion. In the event that one or more subjects are treated for multiple lesions, then a generalized estimating equation with a logistic link function will be used to estimate the 95% confidence interval of the success rate.

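### The Per Protocol set, the only effectiveness population, admits only complete EndoRotor-alone resections, so the resection part of Technical Success is 100% by construction

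*Combined protocol and SAP*

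**What the plan says.** Section 4.1 defines Technical Success by two conditions. The EndoRotor must resect the recurrent lesion without another resection modality, and there must be no definitely or probably device-related SAE through the 90-day follow-up.

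Section 8.2 defines Per Protocol as "those subjects who had complete lesion resection with the EndoRotor alone without any adjunctive modality resection", who also had no eligibility deviation and completed the 90-day visit. It then states: "The effectiveness analyses will be conducted on the per protocol population". The Protocol Summary agrees, under Primary Analysis: "The Per Protocol (PP) analysis population will be the primary" effectiveness set. Section 8.4 places the primary analysis on Per Protocol, describes its members as "treated with the Interscope device without adjunctive modality", and uses the same set for the secondary endpoints. Section 8.4 also says: "The analysis will be conducted on the percent of lesions with persistent disease".

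The Intent to Treat set is "All subjects in whom the EndoRotor was used for any resection of a lesion", including subjects who also received another modality. No effectiveness analysis is assigned to it; section 8.5 uses it only to define the safety population.

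Section 5.7 foresees resections that cannot be finished with the device, in which case "the investigator may convert to the use of an alternative resection modality". Section 5.3 foresees attempts aborted without any tissue being resected.

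**The concern.** Entry to the analysis set depends on the outcome being measured. A subject whose lesion could not be cleared by EndoRotor alone is a failure under section 4.1 but is not in the set on which section 4.1 is evaluated. The reported rate therefore cannot show how often the device resects these lesions unaided, although that ability is the named primary endpoint and section 3.1 says the study will demonstrate effectiveness. No other planned analysis supplies the answer. A reader would see a rate near 100% with a narrow interval and could take it for device performance.

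**Working it through.** **The plan's own figure.** Section 8.8 assumes n = 60 and a success rate of 0.85, and states an exact 95% interval of 0.782 to 0.967 with half width 0.0972. Clopper-Pearson for 51/60 gives 0.734 to 0.929, half width 0.0974. The half width agrees to 0.0002, but the stated limits do not belong to 51/60; they match 45/50. That is a separate error and does not affect this point.

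**Who is in which set**

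| Subject | Technical Success (4.1) | Intent to Treat (8.2) | Per Protocol (8.2) |
|---|---|---|---|
| Complete, EndoRotor alone, no device-related SAE | success | in | in |
| Complete, EndoRotor alone, device-related SAE | failure | in | in |
| Converted to another modality | failure | in | out |
| Attempt aborted, no tissue resected | failure | out | out |

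The in entries for Per Protocol assume no eligibility deviation and a completed 90-day visit. For k Per Protocol subjects the resection component is k/k = 100% for any k.

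**Size.** The unit is the subject, with no loss to follow-up and no eligibility deviations. Let c be the share of attempted subjects not completed with EndoRotor alone, and s the device-related SAE proportion among those completed.

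- All-attempted rate = (1 - c)(1 - s)
- Per Protocol rate = 1 - s = all-attempted rate / (1 - c)

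The inflation factor is 1/0.95 = 1.05 at c = 5%, 1/0.85 = 1.18 at 15% and 1/0.75 = 1.33 at 25%, whatever s is. These values of c are assumed. Section 1.3.2 reports completeness of removal of 73-100% for polypectomy in general, that is 0-27% incomplete, but not for this device or for scarred recurrences.

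| Assumed scenario | All attempted (exact 95% CI) | Per Protocol (exact 95% CI) |
|---|---|---|
| 60 attempted, 3 not completed, no SAE | 57/60 = 95.0% (86.1-99.0) | 57/57 = 100% (93.7-100) |
| 60 attempted, 9 not completed, no SAE | 51/60 = 85.0% (73.4-92.9) | 51/51 = 100% (93.0-100) |
| 60 attempted, 15 not completed, no SAE | 45/60 = 75.0% (62.1-85.3) | 45/45 = 100% (92.1-100) |
| 60 attempted, 9 not completed, 2 SAEs among the other 51 | 49/60 = 81.7% (69.6-90.5) | 49/51 = 96.1% (86.5-99.5) |
| 71 attempted to reach 60 Per Protocol, no SAE | 60/71 = 84.5% (74.0-92.0) | 60/60 = 100% (94.0-100) |

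**The 90-day visit rule.** If one of the two SAE subjects in the fourth row misses the visit, a known failure is removed and Per Protocol becomes 49/50 = 98.0%. Subjects with no known failure who miss the visit are removed too, so the net direction of this rule is not fixed.

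**Fit of the 0.85 planning value.** If 0.85 refers to Technical Success in 60 Per Protocol subjects, it needs 0.15 x 60 = 9 subjects with a definite or probable device-related SAE. The binomial probability of 9 or more is below 0.001 at an assumed risk of 2%, 0.003 at 5%, 0.14 at 10% and 0.56 at 15%. The documents give no device-related SAE rate, so this is unlikely but not excluded.

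**Interval method.** Section 8.4 wants an interval for successful removal of all lesions, by logistic GEE if any subject has several lesions. In a set where every lesion was removed by definition, that model has no finite estimate.

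**The case against.** Several points can be made for the plan.

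- Section 8.4 describes its set without the word complete, so on that wording an incomplete EndoRotor-only case could stay in and count as a failure. This is true, but section 8.4 also names Per Protocol, which section 8.2 defines, and its own wording still removes every conversion.
- Section 8.4 says the analysis concerns persistent disease, which can vary within Per Protocol, and section 8.8 does not say which success rate 0.85 is. The argument about 0.85 is therefore conditional. Persistence is not Technical Success, however, and the plan does not reconcile the two.
- The conversion rate may be low, since exclusion criterion 4 already removes synchronous lesions that would need another modality. At 5% the factor is only 1.05. That changes the size, not the direction.
- The exact factor is a subject-level result. In a lesion-level analysis a converted subject may contribute some successful lesions, so the factor and the direction for the composite are not guaranteed. The resection component stays at 100%.
- The study is single-arm and mainly descriptive, with no test or performance goal, so no formal decision depends on the rate. A descriptive success rate still needs a denominator that contains the failures.

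**Conclusion.** The concern holds. By the definition in section 8.2, the resection component of Technical Success cannot fail in the only population assigned to effectiveness. The endpoint as a whole is not fixed at 100%, because the SAE component can still fail; within Per Protocol the rate is 1 minus the device-related SAE proportion. At subject level, removing conversions can only raise the rate, by a factor of 1/(1 - c). The size depends on c, which the documents do not give. The structural conclusion does not depend on any assumed figure. This must be fixed before analysis, because the primary result as planned does not measure what section 4.1 names.

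**What to change.** In the Protocol Summary and sections 8.2 and 8.4:

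- Define the primary Technical Success set as all eligible subjects in whom EndoRotor resection was attempted, including attempts aborted without tissue removal. State that a subject cannot be reclassified as a screen failure under section 5.3 once resection has been attempted.
- Count as failures any conversion to another resection modality, any resection not completed with EndoRotor alone, and any definite or probable device-related SAE. State whether EndoRotor-only completion at the second visit permitted in section 5.7 counts as success.
- Count a known failure whether or not the 90-day visit took place. Add a sensitivity analysis, labelled worst case, with unknown outcomes as failures.
- Remove the complete-resection condition from Per Protocol and keep that set as supportive.
- Reconcile the persistent-disease sentence in section 8.4 with Technical Success, and state whether the unit is the subject or the lesion.
- Report resection completeness for all attempted subjects. Persistence and stenosis at 90 days may stay on an EndoRotor-only set if it is labelled a selected subset.
- Say what the 60 evaluable subjects are, and restate section 8.8 for that set. At 51/60 the half width of 0.0974 meets the 0.10 target; at 45/60 it is (0.853 - 0.621)/2 = 0.116 and does not.

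The cost is mainly wording. Section 5.7.1 already records whether the device achieved the attempted resection, and converted or aborted cases are failures without 90-day data. Section 5.7.1 lists no separate item for conversion or for the second-visit outcome, so the case report form should be checked for both. Aborted cases exit at discharge and need no extra follow-up. The downside for the sponsor is a less favourable reported rate.
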